## 5. TRIAL POPULATION AND DESCRIPTIVE ANALYSES

### 5.1 Representativeness of Study Sample and Patient Throughput

### 5.2 Withdrawal from treatment and/or follow-up

Withdrawals/losses to follow-up together with reasons will be reported. Any occurrences of participants withdrawing before receiving study intervention and being replaced in study with a new participant will be reported.

### 5.3 Patient Demographic and Clinical Characteristics

There is no randomisation so “baseline comparability of randomised groups” is not applicable. Demographic and clinical characteristics of consenting patients will be summarised.

**Table 1:** Baseline characteristics of all participants

	N	Mean (SD)
Age	XX	XX.XX (X.XX)
	N	%
Gender	XX	XXX
Female	XX	XX.XX
Male	XX	XX.XX
Site	XX	XXX
1	XX	XX.XX
2	XX	XX.XX
3	XX	XX.XX
4	XX	XX.XX
5	XX	XX.XX
6	XX	XX.XX
7	XX	XX.XX
8	XX	XX.XX
9	XX	XX.XX
10	XX	XX.XX
11	XX	XX.XX

**Table 2:** Clinical characteristics of all participants

	N	%
Dysphagia level	XX	XXX
Able to eat normal diet / no dysphagia	XX	XX.XX
Able to swallow some solid foods	XX	XX.XX
Able to swallow only semi-solid foods	XX	XX.XX
Chemoradiotherapy	XX	XXX

	N	%
Definitive chemoradiotherapy	XX	XX.XX
Neo-adjuvant chemoradiotherapy	XX	XX.XX

**Table 3:** Tumour characteristics of all participants

	N	%
Tumour site	XX	XXX
Lower thoracic oesophagus	XX	XX.XX
Middle thoracic oesophagus	XX	XX.XX
Oesophagogastric junction	XX	XX.XX
Upper thoracic oesophagus	XX	XX.XX
Tumour type	XX	XXX
Adenocarcinoma	XX	XX.XX
Squamous cell carcinoma	XX	XX.XX
T stage	XX	XXX
T1	XX	XX.XX
T2	XX	XX.XX
T3	XX	XX.XX
T4	XX	XX.XX
N stage	XX	XXX
N0	XX	XX.XX
N1	XX	XX.XX
N2	XX	XX.XX
M stage	XX	XXX
M0	XX	XX.XX
M1	XX	XX.XX

#### 5.4 Unblinding

Not applicable.

## 5.5 Description of Compliance with Intervention

The number of eligible, consented patients who complete the Cytosponge™ procedure overall and in each subgroup (having received dCRT and naCRT) will be reported. The number of eligible patients who return the questionnaire and have a telephone interview at one and two weeks (i.e. those who do not have surgery in the two weeks after the Cytosponge™ procedure) will also be reported. Deviations from intended treatment (non-adherence to protocol) including losses to follow-up and withdrawals will be summarised.

## 5.6 Reliability

Any calculations performed using the computer will be checked by hand for the smallest of 5% or 20 observations within the dataset, where appropriate. It is not expected that any data derivation / manipulation will be required. If any should need to take place, the reasons for these will be given and the validity of the derived data will be checked.

## 6. ANALYSIS

### 6.1 Definitions of feasibility outcomes

#### 6.1.1 Primary feasibility outcome

The primary outcome measure is the completion rate, defined as the proportion of consented, evaluable participants who are able to successfully undergo the Cytosponge™ procedure. i.e. patients who are able to swallow the sponge and have the sponge retrieved without additional intervention. Evaluable participants are those who have attempted to swallow the Cytosponge™.

#### 6.1.2 Secondary feasibility outcomes

**Safety:** defined as all serious adverse events (including bleeding requiring transfusion and perforation) that occur between from the time of Cytosponge™ administration (D1) and when the patient completes the study at the two week telephone follow-up. If a participant undergoes surgery prior to their two week follow up visit, then their safety reporting period continues until the time of surgery. Adverse events will also be reported. Severity rating of adverse effects will be as per the Common Terminology Criteria for Adverse Events (CTCAE) V4.03.

**Consent rate:** defined as the proportion of eligible patients who consent to take part in the study.

**Acceptance rate:** defined as the proportion of patients who have successfully undergone the Cytosponge™ procedure and would be prepared to accept the procedure repeatedly if it was to be used for follow-up.

**Suitability of sample for biomarker analysis:** defined as the percentage of samples from the Cytosponge™ test with the presence of cytological atypia and/or p53 abnormality (also called “positive samples”).

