3 OBJECTIVES AND ENDPOINTS

Primary Objective	Endpoint
Completion rate	The proportion of consented, evaluable, patients successfully undergoing Cytosponge™ will be presented, with the corresponding 95% confidence interval. The proportion will be calculated overall and separately for those having dCRT and naCRT.
Secondary Objectives	Endpoints
Safety	All serious adverse effects related to the procedure, including bleeding (requiring transfusion) and perforation*
Suitability of sample for biomarker analysis	Quality of material obtained from Cytosponge™ test will be centrally analysed at Cambridge (cellularity, yield and quality of extracted DNA will be used as measure of quality). A positive Cytosponge™ result will be defined as presence of cytological atypia and/or p53 mutation
Acceptance rate	
 1. Proportion of eligible patients approached who consent 2. Proportion of patients who have successfully undergone the procedure & would be prepared to accept the procedure repeatedly if it was to be used for follow-up (data will be captured through questionnaire after procedure)
Tertiary Objectives	Endpoints
Residual disease markers	Level of ctDNA in responders vs non-responders
Cytosponge™ comparative efficacy to biopsy	Level of residual cancer, p53 mutations & other identifiable markers in Cytosponge™, pre & post- treatment biopsies

* A TMG meeting will be called if there are >3 cases of procedure related bleeding requiring a blood transfusion.

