11.1 Adverse Event Definitions

An **Adverse Event or experience (AE)** is any untoward medical occurrence in a study participant temporally associated with the administration of a medical device, whether or not considered caused by or related to the medical device. An AE can therefore be any unfavourable and unintended sign, symptom, disease (new or exacerbated) and /or significant abnormal laboratory or physiological observation temporally associated with the use of a medical device. For marketed medicinal products, this also includes failure to produce expected benefits (i.e. lack of efficacy), abuse or misuse.

An **Adverse Device Effect (ADE)**, as it relates to the use of the Cytosponge™ procedure, is defined as including an untoward medical occurrence resulting from: insufficiencies or inadequacies in the instructions for use, deployment, implantation, installation, operation, or any malfunction, a user error or intentional misuse.

A **Serious Adverse Event (SAE)** is any AE, regardless of causality or expectedness, that:

• Led to death	
• Led to a serious deterioration in health that either:	
○ Resulted in a life-threatening illness or injury.	This refers to an event in which the subject was at risk of death at the time of the event. It does not refer to an event, which

	hypothetically might have caused death, if it were more severe resulting in a permanent impairment of a body structure or a body function.
○ Resulted in permanent impairment of a body structure or a body function.	
○ Requires in-patient hospitalisation or prolongation of existing hospitalisation.	In general, hospitalisation signifies that the subject has been admitted (usually involving at least an overnight stay) at the hospital or emergency ward for observation and/or treatment that would not have been appropriate in the physician's office or out-patient setting. Complications that occur during hospitalisation are AEs. If a complication prolongs hospitalisation or fulfils any other serious criteria, the event is serious. When in doubt as to whether hospitalisation occurred or was necessary, the AE should be considered serious. Any hospitalisation that was planned before trial entry, or a planned hospitalisation for a pre-existing condition, without serious deterioration in health, will not meet SADE criteria.

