## 6.2.2 Analysis of secondary feasibility outcomes

### Safety

All Adverse Events (AEs) and Serious Adverse Events (SAEs) will be summarised using the safety population. As the Cytosponge™ is an Investigational Medical Device, additional adverse event categorisation – of Adverse Device Effect (ADE), Serious Adverse Device Effect (SADE), and Unanticipated Serious Adverse Device Effect (USADE) – is required. Serious Adverse Events related to the procedure and any events recorded as ADE, SADE, or USADE will be summarised over the follow-up period i.e. from the time of Cytosponge™ administration (D1) until the patient completes the study at the two week telephone follow-up, or until the time of surgery if the patient is operated on within the follow-up period.

Telephone follow-up interviews will not be undertaken after surgery. If an Investigator reports any study intervention related SADEs following the two week follow up period (as noted in Protocol V3.0), these will also be included in the summaries. Summaries will be in tabular form. It is intended that the number and percentage of patients experiencing SAEs overall, will be presented by treatment group (naCRT/dCRT). SAEs, SADEs, and USADEs will be grouped by system organ class (SOC) and according to whether they occurred on the day of the procedure or later.

In addition, all AEs and ADEs will be summarised in tabular form. It is intended that the number and percentage of patients experiencing AEs and ADEs will be presented overall and according to causality (treatment-relatedness). The AEs may be split by grade (1-2 and 3+) and presented by SOC and according to whether they occurred on the day of the procedure or later. These descriptive summaries will be based on the safety population.

**Consent rate** (agreement to undergo procedure), defined as the percentage of eligible patients who consent to participate in the study. Any patients who consent but withdraw their consent prior to the Cytosponge™ procedure will be considered not to have consented. The percentage will be presented together with the corresponding 95% confidence interval.

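### SAP 6.1.2 defines the safety outcome as all-cause SAEs, in conflict with Protocol section 3 and SAP 2.2, and SAP 6.2.2 specifies no patient percentage or interval for procedure-related SAEs

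*SAP*

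**What the plan says.** **Endpoint.** Protocol section 3 gives the safety endpoint as "All serious adverse effects related to the procedure, including bleeding (requiring transfusion) and perforation". SAP 2.2 repeats it.

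**Definition for analysis.** SAP 6.1.2, the section that defines the outcomes, has safety "defined as all serious adverse events (including bleeding requiring transfusion and perforation"), counted from administration to the two-week call or to surgery if earlier. It says nothing about relatedness. Protocol 11.1 states that an SAE "is any AE, regardless of causality or expectedness, that" meets a seriousness criterion, so the term is all-cause.

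**Analysis.** SAP 6.2.2 (Safety) makes four relevant statements:
- On related events: "Serious Adverse Events related to the procedure and any events recorded as ADE, SADE, or USADE will be summarised over the follow-up period". The form is tabular; the statistic is not stated.
- On a patient-level figure for serious events: "the number and percentage of patients experiencing SAEs overall, will be presented by treatment group (naCRT/dCRT").
- On layout, with the procedure day set against any time after it: "SAEs, SADEs, and USADEs will be grouped by system organ class (SOC) and according to whether they occurred on the day of the procedure or".
- On AEs and ADEs: "the number and percentage of patients experiencing AEs and ADEs will be presented overall and according to causality (treatment-relatedness").

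**Intervals.** SAP 4.1 says in general that 95% confidence intervals will be reported. SAP 6.2.2 names one for the consent rate, names none for safety, and calls the safety summaries descriptive.

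**The concern.** The safety question in this study is what harm the sponge does in an oesophagus that has had chemoradiotherapy. Protocol 1.3 says that no safety data exist for the device in carcinoma patients after dCRT. An all-cause SAE percentage does not estimate that risk, because it also counts serious events with no link to the procedure. An analyst who follows 6.1.2 to the letter would report a different quantity from the one that Protocol section 3 and SAP 2.2 name.

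The result also has a use. Protocol 14.5 and the matching text in SAP 3.7 make the move to a later trial depend on whether the primary and secondary objectives are met. If the related events appear only as counts by organ class and timing, a low or zero count carries no statement of how much risk 50 patients leave open.

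**Working it through.** **1. The plan's own figure.** The documents give no design figure for safety. The only precision figure is for the completion rate (Protocol 13.1, SAP 3.3): n = 50, rate 70%, asymptotic 95% CI of ±13%.

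Half-width = 1.96 × √(0.70 × 0.30 / 50) = 1.96 × 0.0648 = 0.127, which rounds to 13%. It reproduces.

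**2. The texts side by side.**

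| Place | Serious events covered | Patient n (%) specified? | Interval named? |
|---|---|---|---|
| Protocol section 3, SAP 2.2 | Procedure-related | Not stated | No |
| SAP 6.1.2 | All-cause | Not stated | No |
| SAP 6.2.2, SAEs | All-cause | Yes, by naCRT/dCRT | No |
| SAP 6.2.2, related SAEs, SADEs, USADEs | Procedure- or device-related | No; tabulated, by organ class and timing | No |

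The AE and ADE percentages by causality do not fill the empty cell. SAEs are AEs and SADEs are ADEs, but that table may be split by grade and is not split by seriousness. Protocol 11.4 lists mild sore throat as an ADE, and the Risks part of Protocol 1.3 calls sore throat the most common side effect. An ADE percentage would therefore pool sore throat with perforation.

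**3. What an interval adds.** Take the safety population (SAP 4.2: everyone who attempted to swallow the device) as n = 50. The exact (Clopper-Pearson) limits for x patients with a related SAE are the 2.5th percentile of Beta(x, n − x + 1) and the 97.5th percentile of Beta(x + 1, n − x). For x = 0 the upper limit reduces to 1 − 0.025^(1/50) = 0.071.

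| Patients with a related SAE | Estimate | Exact 95% CI |
|---|---|---|
| 0/50 | 0% | 0 to 7.1% |
| 1/50 | 2% | 0.05 to 10.6% |
| 2/50 | 4% | 0.5 to 13.7% |

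**4. How far the all-cause figure could differ.** The documents give no SAE rates, so both inputs are assumptions: u is the risk of an unrelated SAE, d the risk of a related one, taken as independent. All-cause risk is a = 1 − (1 − u)(1 − d). The share of all-cause SAE patients with no related event is 1 − d/a.

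| u | d | a | Share with no related event |
|---|---|---|---|
| 0% | 2% | 2.0% | 0% |
| 2% | 5% | 6.9% | 27.5% |
| 2% | 2% | 4.0% | 49.5% |
| 5% | 2% | 6.9% | 71% |
| 10% | 2% | 11.8% | 83% |
| 20% | 1% | 20.8% | 95% |

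Over u from 0 to 20% and d from 1 to 5%, the share runs from 0% to about 95%. The two definitions can give nearly the same answer or very different ones, and the documents do not say which to expect.

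**The case against.** The best defence is that nothing is lost. SAP 2.2 restates the protocol endpoint, SAP 6.2.2 commits to tabulating related SAEs and SADEs, and the denominator is fixed in SAP 4.2, so anyone who has the count of affected patients can work out the percentage. All-cause capture also fits Protocol 11.7, under which every SAE goes to the MHRA. No numerical rule uses an SAE percentage: the stopping rule and the bleeding trigger count events from the device or procedure, and the only numerical criterion for going on is completion above 70%. Section 3 of the protocol asks for an interval for completion and not for safety, and SAP 4.1 promises 95% intervals in general.

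Most of this stands, and it limits the severity. It also rules out two readings that a reader might infer: that the SAP replaces the protocol's endpoint, and that it gives patient percentages for all-cause SAEs alone. Related events are still analysed, and AEs and ADEs get a percentage by causality.

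The defence does not remove the conflict between 6.1.2 and 2.2. Nor does it guarantee a patient-level figure, since a table by organ class and timing may count events. SAP 4.1 together with the descriptive label in 6.2.2 leaves the interval for related serious events unsettled.

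**Conclusion.** The point holds as a conflict of definitions and a reporting gap. SAP 6.1.2 is broader than the endpoint in Protocol section 3 and SAP 2.2. For serious events, SAP 6.2.2 specifies patient numbers and percentages only for the all-cause version. The interval figures (upper limits of 7.1%, 10.6% and 13.7% for 0, 1 and 2 patients) assume that all 50 planned patients enter the safety population.

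A reader might go further and infer that the reported safety figure would consist mostly of morbidity from the cancer and the chemoradiotherapy. The documents do not support that. They give no SAE rates, Protocol 11.9 exempts events clearly consistent with progression and planned admissions, and observation lasts about two weeks or ends at surgery. Under the assumed rates in the working, the unrelated share can be anything from none to nearly all.

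Severity is moderate to minor, because the related events would still be tabulated.

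**What to change.** - **SAP 6.1.2:** restore the condition that the serious event is related to the procedure, meaning possibly, probably or definitely related under Protocol 11.2.
- **SAP 6.2.2:** report the number and percentage of the safety population with at least one procedure-related SAE, overall and by dCRT/naCRT, with an exact (Clopper-Pearson) 95% CI.
- **All-cause SAEs:** keep them as a supporting table.

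The cost is two sentences in the SAP and one table row. No new data are needed: Protocol 11.2 and 11.8 already require causality for each AE, and SAP 4.2 already defines the denominator.

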Secondary Endpoints	
Safety: All serious adverse effects related to the procedure, including bleeding (requiring transfusion) and perforation will be assessed.
 
Acceptance Rate:
 
 a. Proportion of eligible patients approached who consent b. Proportion of patients who have successfully undergone the procedure & would be prepared to accept the procedure repeatedly if it was to be used for follow-up (data will be captured through questionnaire after procedure) 
Suitability of Sample for Biomarker analysis: Quality of material obtained from Cytosponge™ test will be centrally analysed at Cambridge. A positive Cytosponge™ result will be defined as presence of cytological atypia and/or p53 abnormality.

Tertiary Endpoints	
Level of ctDNA in responders vs non-responders
 
Level of residual cancer, p53 mutations & other identifiable markers in Cytosponge™, pre & post- treatment biopsies.

Study Design	This is a feasibility study involving patients with known oesophageal cancer treated with pre-operative or definitive chemoradiation. All participants will undertake the Cytosponge™ test. The Cytosponge™ will be processed for evidence of residual cancer through analysis of cellular atypia and molecular biomarkers. Where available, the results will be compared with histology.
Patient Numbers	50 evaluable participants
Target Population	Patients who have undergone CRT for oesophageal cancer
Inclusion criteria	
 1. Male or female, age ≥ 16 years who 
 a. have undergone pre-operative CRT as treatment for oesophageal cancer and are due to undergo oesophagectomy or b. have undergone definitive CRT as treatment for oesophageal cancer 2. 4-16 weeks post completion of CRT 3. Dysphagia score 0-2 (Mellow Scale) 4. Able to swallow tablets 5. Physiologically fit for endoscopy 6. Written (signed and dated) informed consent

	7. The patient is willing and able to comply with the protocol for the duration of the study, and scheduled follow-up visits and examinations.

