For the Cytosponge™ to have a wider application in oesophageal cancer, including treatment surveillance, a feasibility study is required. One of the important differences from patients with BE is that these patients already have dysphagia which could make swallowing of the capsule or retrieval of Cytosponge™ more difficult. Secondly, radiotherapy would have resulted in inflammation of the surrounding tissue. Sample analysis should be robust enough to differentiate molecular markers of inflammation from that of residual cancer. Finally, although a molecular marker for BE and dysplasia that can be detected by Cytosponge™ is well defined and assessed through immunohistochemistry Trefoil Factor 3 (TFF3) and p53 sequencing, markers for invasive cancer detectable with this device need to be developed and validated.

Benefits

This study will test the acceptability and feasibility of using Cytosponge™ post chemo-radiation. The participants will not benefit directly. However, if this study shows feasibility/acceptability, it will lead to larger studies evaluating its role in surveillance post-dCRT, using the Cytosponge™ at multiple time-points during follow-up. An effective surveillance programme may detect a greater proportion of patients with local-only recurrences treatable by curative salvage resection. It may also lead to a shift in standard care where patients could be offered dCRT as first choice, keeping surgery in reserve for patients who fail dCRT.

Risks

The risk for Cytosponge™ in patients with oesophageal cancer has not been assessed previously. It has however, been tested in >1000 patients with Barrett's esophagus. The most common side-effect is a sore throat. Rare complications could be bleeding, perforation, effects on the airway, the Cytosponge™ getting stuck beyond the tumour or detachment of the Cytosponge™ from the string requiring endoscopy to recover the Cytosponge™.

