7.2 Samples to be sent to and analysed in a Central Laboratory

All Cytosponge™ specimens will be couriered to the [name] Laboratory, at the MRC Cancer Unit. Cytosponge™ specimens will be processed in conjunction with the Cambridge University Hospitals' NHS Foundation Trust tissue bank which is accredited to GLP standards [10]. Samples will be processed to a paraffin embedded cell clot, sectioned and stained with Haematoxylin and Eosin (2 levels) and for immunohistochemical markers (TFF3 if adenocarcinoma, p53 in all cases) using a DAKO autostainer according to GCP standards. An expert GI cytologist will verify any atypia and positive immunostaining. In addition, DNA will be extracted for p53 sequencing using a multiplex assay as previously described and for ploidy status. Although timely processing will ensure that the study completes on time the results of Cytosponge™ samples will not affect patient clinical care since it is not being used as a diagnostic tool in the trial, and therefore there is some flexibility in the timeline. The biomarkers will be scored according to previously optimised protocols [10, 13-15]. These data will be compared to the degree of dysplasia determined from endoscopic biopsies or surgical specimen where surplus material is available as a result of routine care procedures. For further details, please refer to the Device & Sample Handling Manual.

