## 2.2 Objectives

Primary Objective	Endpoint
Completion rate	The proportion of consented, evaluable, patients successfully undergoing Cytosponge™ will be presented, with the corresponding 95% confidence interval. The proportion will be calculated overall and separately for those having dCRT and naCRT.
Secondary Objectives	Endpoints
Safety	All serious adverse effects related to the procedure, including bleeding (requiring transfusion) and perforation.
Suitability of sample for biomarker analysis	Quality of material obtained from Cytosponge™ test will be centrally analysed at Cambridge (cellularity, yield and quality of extracted DNA will be used as measure of quality). A positive Cytosponge™ result will be defined as presence of cytological atypia and/or p53 mutation
Acceptance rate	
 
1. Proportion of eligible patients approached who consent
 
2. Proportion of patients who have successfully undergone the procedure & would be prepared to accept the procedure repeatedly if it was to be used for follow-up (data will be captured through questionnaire after procedure)
 

Tertiary Objectives	Endpoints
Residual disease markers	Level of ctDNA in responders vs non-responders
Cytosponge™ comparative efficacy to biopsy	Level of residual cancer, p53 mutations & other identifiable markers in Cytosponge™, pre & post- treatment biopsies

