### 4.2 Definition of Analysis Populations

**Population for assessment of completion rate:** all patients who have provided consent and have attempted to swallow the Cytosponge™.

**Population for calculation of consent rate:** all patients who consented, out of all those patients who were eligible.

**Population for assessment of acceptance rate:** all patients who successfully undergo the Cytosponge™ procedure.

[figure not shown]
**Population for assessment of suitability of sample:** all samples (taken during the Cytosponge™ procedure) sent to Cambridge for analysis.

**Safety population:** all participants who attempted to swallow the Cytosponge™.

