**Acceptance rate** (acceptance to repeat procedure), defined as the percentage of patients who have successfully undergone the Cytosponge™ procedure and would be prepared to accept the procedure repeatedly if it was to be used for follow-up. A questionnaire will be given to each patient, to be completed after the procedure. The questionnaire will either be completed just after the procedure or, if the patient cannot stay, completed later and returned by post.

**Suitability of sample for biomarker analysis**, defined as the percentage of samples from the Cytosponge™ test with the presence of cytological atypia and/or p53 abnormality (also called “positive samples”). Quality of material obtained from the Cytosponge™ test will be centrally analysed at Cambridge. Cellularity, yield and quality of extracted DNA will be used as measure of quality. Data for these analyses are not expected to be available with the data for the primary outcome and the acceptance- and safety-related secondary outcomes; biomarker analyses will therefore be conducted and reported separately.

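### The SAP measures sample suitability by the percentage of positive samples, so an adequate negative sample counts as unsuitable

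*SAP*

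**What the plan says.** SAP 6.1.2 states that suitability of the sample for biomarker analysis is "defined as the percentage of samples from the Cytosponge™ test with the presence of cytological atypia and/or p53 abnormality". SAP 6.2.2 repeats the definition as the analysis method, so it is not an isolated slip. SAP 4.2 sets the population as "all samples (taken during the Cytosponge™ procedure) sent to Cambridge for analysis".

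The endpoint tables describe something else. Protocol section 3 makes the endpoint the quality of the material and specifies that "cellularity, yield and quality of extracted DNA will be used as measure of quality". SAP 2.2 carries the same row. In both tables a separate sentence defines a positive result; in SAP 2.2 it reads "A positive Cytosponge™ result will be defined as presence of cytological atypia and/or p53 mutation". The secondary endpoints in the protocol synopsis likewise put sample quality and the definition of positivity under one heading. Neither document says in these tables that suitability means positivity.

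SAP 6.2.2 returns to quality immediately after its positivity definition: "Cellularity, yield and quality of extracted DNA will be used as measure of quality". It gives no adequacy criterion, proportion, mean, median or interval for these measures, and it defers the biomarker analyses to separate reporting.

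**The concern.** Suitability for biomarker analysis asks whether the sponge yields material that can be read and sequenced. Positivity asks what the reading shows. The protocol keeps these apart in its objectives: objective 4 is suitability, and objective 6 is comparative efficacy in identifying residual cancer. The SAP definition answers something close to objective 6, which SAP 6.5 already addresses by comparing the proportion positive with post-treatment biopsy. Objective 4 is left without a valid summary.

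The definition can also point the wrong way. Protocol 1.3 envisages detecting new abnormality in an oesophagus cleared by chemoradiotherapy. In a cleared patient an adequate negative sample is the expected finding, yet here it lowers suitability. The same section warns that inflammation after radiotherapy must be distinguished from residual cancer. Inflammatory change read as atypia would raise suitability.

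Protocol section 20 says that it is not yet clear what material the device will provide in this setting. This endpoint should answer that question. It also feeds, in general terms, into progression, because Protocol 14.5 and SAP 3.7 make the move to phase II depend on the primary and secondary objectives being met.

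**Working it through.** **The plan's own figure.** The only design figure concerns the completion rate (Protocol 13.1, SAP 3.3): 1.96 × √(0.70 × 0.30 / 50) = 0.127, which agrees with the stated ±13%. No figure is given for sample suitability, so what follows is an illustration.

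**What follows from the wording alone.** The denominator is every sample sent and the numerator is positive samples only. An adequate negative sample and an inadequate sample are both in the denominator and both outside the numerator, so the percentage cannot separate them. This needs no numerical assumption.

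**Inputs for the illustration.**
- Complete pathological response (pCR) of 25–49%: Protocol 1.1. This is a background range, not a forecast for this mix of definitive and neo-adjuvant patients.
- Test accuracy: a perfect test, and three sensitivity/specificity pairs built from Protocol 1.3. The pair 100%/97% is reported for squamous dysplasia. The pairs 90%/94% and 73%/92% come from the Barrett's ranges of 73–90% and 92–94%. Those ranges were obtained with TFF3, a different marker from atypia or p53, and the pairing of their ends is mine. None was measured after chemoradiotherapy.
- Adequacy: 100%, and 80% as an assumption.
- Positivity is taken to track residual disease, adequacy to be unrelated to disease status, and inadequate samples never to be positive.

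**Formula.** SAP figure = adequacy × [(1 − pCR) × sensitivity + pCR × (1 − specificity)].

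With adequacy 100%:
- Perfect test: 0.75 = 75.0% at pCR 25%; 0.51 = 51.0% at pCR 49%.
- 100%/97%: 0.75 + 0.25 × 0.03 = 75.8%; 0.51 + 0.49 × 0.03 = 52.5%.
- 90%/94%: 0.75 × 0.90 + 0.25 × 0.06 = 69.0%; 0.51 × 0.90 + 0.49 × 0.06 = 48.8%.
- 73%/92%: 0.75 × 0.73 + 0.25 × 0.08 = 56.8%; 0.51 × 0.73 + 0.49 × 0.08 = 41.2%.

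For 80% adequacy each value is multiplied by 0.8:

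| Test | SAP figure, 100% adequate | SAP figure, 80% adequate |
|---|---|---|
| Perfect | 51–75% | 41–60% |
| 100%/97% | 52–76% | 42–61% |
| 90%/94% | 49–69% | 39–55% |
| 73%/92% | 41–57% | 33–45% |

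**Same figure, different adequacy.** The adequacy at pCR 25% that gives the same SAP figure as 100% adequacy at pCR 49% is the ratio of the two values:
- Perfect test: 51.0/75.0 = 0.68.
- 100%/97%: 52.47/75.75 = 0.69.
- 90%/94%: 48.84/69.0 = 0.71.
- 73%/92%: 41.15/56.75 = 0.73.

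**Sampling error does not hide the gap.** With an assumed 35 samples (70% of 50), 18 positive gives 51% (exact 95% CI 34–69%). If all 35 are adequate, adequacy is 100% (90–100%).

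**The case against.** The strongest defence is that no data are lost. SAP 6.2.2 says that material quality will be analysed centrally and names the measures, so the ambiguity arises only if the percentage is read without them. Scoring follows laboratory protocols and a Device & Sample Handling Manual (Protocol 7.2) that are not available here and may contain adequacy cut-offs. This stands in part: the claim that no summary exists applies to the Protocol and SAP only. It does not rescue the definition, because the stated numerator remains positivity, and deferring the biomarker analyses supplies no other one.

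A second objection is that the numerical illustration is weakly founded. The lower ranges rest on the TFF3 Barrett's figures, and the squamous dysplasia figures give almost the perfect-test range. Comparison with biopsy or surgical specimens would also narrow the uncertainty about pCR. Protocol 1.3 itself says that "markers for invasive cancer detectable with this device need to be developed and validated". This is fair. The numbers show direction and possible size only, and the defect does not depend on them.

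A third objection is timing. The SAP is dated 22 April 2020 and recruitment ended on 31 January 2020, so criteria can be set in advance only if samples had not been scored. SAP 6.2.2 indicates that the biomarker data were still to come, which makes the change feasible, although it does not prove that no results had been seen.

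Finally, the endpoint is secondary and descriptive, and the only numerical trigger for progression is a completion rate above 70%. That is correct and limits the importance of the point.

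**Conclusion.** The concern holds. The SAP definition departs from the endpoint in Protocol section 3 and in the SAP's own section 2.2, and it counts adequate negative samples as unsuitable. The protocol invites the confusion by putting positivity in the same row, but only the SAP equates the two.

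Under the assumptions above, a study in which every sample is adequate would report a suitability of 51–75% with a perfect test, and a reported 51% would fit either 100% or 68% adequacy. If positivity does not track residual disease, the documents support no range, but the percentage still does not measure adequacy.

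This should be fixed, though its effect on decisions is limited. The primary endpoint is unaffected, and the endpoint reaches the progression decision only through the general condition on secondary objectives. Even its availability for that decision is unsettled: SAP 3.5 assesses all secondary outcomes at one time point, while SAP 6.2.2 reports the biomarker analyses separately.

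**What to change.** - **Numerator (SAP 6.1.2 and 6.2.2).** Define suitability as the proportion of samples meeting laboratory adequacy criteria set before results are seen, whether the result is positive or negative. Keep the SAP 4.2 denominator and give a 95% confidence interval.
- **Two figures.** Report adequacy for cytology and immunostaining (cellularity) and for sequencing (DNA yield and quality) separately. Protocol 7.2 plans both, including that "DNA will be extracted for p53 sequencing using a multiplex assay as previously described and for ploidy status".
- **Positivity.** State that the positivity sentence in the endpoint tables and the protocol synopsis defines a result, not suitability. Report the percentage positive as a separate result beside the SAP 6.5 comparison with biopsy.
- **Wording of p53.** The synopsis has "presence of cytological atypia and/or p53 abnormality", as do SAP 6.1.2 and 6.2.2, whereas Protocol section 3 and SAP 2.2 refer to mutation. Use one term throughout.

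The cost is SAP wording and laboratory input on cut-offs. If cut-offs already exist in the laboratory protocols or the manual, the SAP need only cite them. The quality measures are already planned, so no new patient procedures are needed. The final report would carry two adequacy figures in place of one percentage, and a short clarifying note to the protocol's endpoint wording would be tidy.
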